
Recruitment and feasibility. Total enrollment for the study will be 108 participants per site (54 ME-CCT and 54 SC per site), for a total of 216 participants (108 ME-CCT and 108 SC). Participants will be primarily recruited through clinic referrals and medical record review followed by recruitment letters sent to patients who meet the requisite pre-screening criteria. The recruitment letter will state that the individual may opt out by calling the research team indicating that they do not wish to be contacted, or they may indicate they are interested in learning more about the study by calling the study team. The letter will state that if the individual has not responded to the letter within two weeks, research personnel will contact them by phone. Participants will also be recruited through other research study referrals and contacted by letter /phone (see Section 11: Recruitment for more recruitment methods). We will recruit a sample composed of at least 25% of individuals from ethnic/racial minority groups, including African Americans, consistent with the 2013 US Census. This will provide us with enough subjects to explore minority status as a moderator of treatment outcome, although we do not expect differential effects. By having two sites, we will be better able to ensure adequate ethnic/racial diversity in our sample. We will recruit women and men. At the VASDHS, over the past year approximately one third of the 500+ total referrals to the Neuropsychological Assessment Unit were diagnosed with MCI and likely would have been eligible for the proposed study. At VAPORHCS, 2,472 Veterans with a diagnosis of MCI were treated over the past two years; moreover, within the past year, of the 336 neuropsychological assessments conducted through the VAPORHCS Neuropsychology Clinic, 129 of those (59%) resulted in a diagnosis of MCI and likely would have been eligible to participate in the proposed study. At the VAPORHCS, since January 2015, 125 patients have been referred for the waiting list for the ME-CCT intervention; all referrals came from clinicians who had heard about the groups through word of mouth. We did not implement any intensive research recruitment efforts such as those proposed in this study (e.g., advertisements, letters to eligible patients, study compensation, study coordinators with protected time to seek out referrals). This demonstrates not only recruitment feasibility but also genuine interest in the groups, both by patients and the clinicians who refer them. Based on these data, we estimate that over 250 adults per year will be eligible to participate in the proposed study between the two sites, indicating that the goal of recruiting 216 participants over the course of the five-year study is very feasible. Nevertheless, should our VA recruitment efforts prove less successful than we anticipate,

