Procedures. Potential subjects will be identified through the specific recruitment methods described in the below section 11. Prior to enrollment, interested Veterans will be **pre-screened**. Study personnel will conduct a medical record review, including neuropsychological assessment records, to ensure study eligibility. As described in the following sections related to recruitment (Section 9: "Recruitment and Feasibility" and Section 11: "Recruitment"), study personnel will then contact individuals by phone or letter, depending on the specific recruitment method, to answer questions about the study, confirm interest in participation, and to schedule an initial study visit. All eligible participants will then complete an **initial study visit** which will include **informed consent** and **baseline measures** (see **Table 5**); all participants will be carefully screened to ensure their ability to comprehend study procedures, risks and benefits. Participants at the VASDHS site will be offered the opportunity to use a Fitbit to track their physical activity and sleep during the study. (The Fitbit Charge 2 is a non-invasive, water-resistant, wrist-worn device that measures steps taken, distance traveled, heart rate, and sleep quality and stages.) Upon enrollment, we will create a unique login ID and password for each participant to enable us to track their data on the Fitbit website each week of the 8-week intervention; we will upload these data during the weekly group session. When connected to a compatible device (i.e., study computer), data are automatically uploaded to the users' Fitbit accounts. The researchers will bring a study laptop to the groups each week, at which time the researchers will upload participants' data for adherence and assessment purposes. These data will then be "dumped" into and stored on a secure study server. We will also upload their data during their last assessment at 21 weeks; however, participants will be given the option of coming to the VA between the 8 week and 21 week assessment to upload their data so they can get continued summary of their progress each week. The participants will be allowed to keep the device when the study ends and guided through the procedure for establishing a new username and password, thereby terminating the research staff's access to their account. All eligible participants will then be **randomized** to either the ME-CCT or SC group. Randomization tables will be prepared by [name], the study statistician, at the beginning of the study. For each site, groups will be randomly assigned to ME-CCT or SC based on the site's randomization table. New study participants will be allocated to the current group awaiting randomization. Once group membership reaches the minimum of 6, the group will be randomized by [name], who will be blind to membership of each group. Randomization procedures and enrollment for each site will be monitored by [name], and if imbalance occurs at any site, he will recommend the necessary adjustment. Following randomization, participants will receive the **intervention (ME-CCT or SC)** for 8 weeks. To reduce the risk of treatment

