Data analyses will proceed in stages: 1) First, descriptive statistics and exploratory analyses will be used to assess the normality of the data and homogeneity of variance. The continuous outcome data will be transformed if necessary by using an appropriate transformation such as the log transform for skewed long tailed data. Similarly, potential covariates will be summarized with descriptive statistics and graphs to determine the most appropriate way to treat these variables. In addition, the results will be inspected for bias due to dropouts or missing data. 2) Although we don't anticipate any baseline differences, we will compare any differences among groups and sites on baseline measures. Any statistically and clinically significant differences will be controlled for in subsequent analyses by adding the target variables as covariates to the model. 3) We propose to use mixed effects modeling to account for clustering structure of the data (i.e., repeated assessments within an individual, groups, therapists and sites) for main hypotheses testing. The mixed effects approach is more powerful than traditional methods and allows the inclusion of subjects with missing data or those who were terminated early in the study, without relying on data imputation procedures. Two specific forms of the mixed effects models of random regression models (RRM), also known as hierarchical linear models (HLM) or multilevel models, and mixed model analysis of variance (MMANOVA) will be considered. Each outcome variable will be graphed versus time for each subject to evaluate what function of time best describes the data. If the change is linear we will proceed with the HLM structure. If the time pattern is not immediately apparent we will proceed with the MANOVA. 4) We will use the extension of the Pattern-Mixture models [89] which allow subject-to-subject heterogeneity, to assess if there is bias due to drop out or missing data. Furthermore, the randomness of missing data will be examined according to recommended procedures [90], which includes comparing group differences in the primary outcomes of subjects with versus without missing data. Specific plans for testing each hypothesis are below.

H1: Compared to those in SC, participants in ME-CCT will show significant improvements in objective cognitive performance and functional capacity.

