Dependent variables: Neurocognitive composite score (Average z score across subtests in the Neurocognitive Battery detailed in **Table 6**); Functional capacity composite score (Average z score across subtests in the Functional Capacity Battery detailed in **Table 7**). **Independent variables:** Treatment group (2 levels, ME-CCT and SC), and Time (4 levels, Weeks 0, 4, 8, 21). **Statistical Analysis:** We will analyze data on all randomized subjects for whom we have a baseline assessment and at least one post-baseline evaluation. Data will be analyzed by mixed effects model methods [91-93] for linear or non-linear trends based on earlier inspection of data. The mixed effects model method provides an estimate of the individual variability around the population trend, the variability of the individual intercepts (baseline values) and slopes (changes across time), and the correlation between them. A fully saturated treatment X time model will be utilized for inference. Covariance structure will be chosen based on Akaike's Information Criterion (AIC). Random group level treatment effects will also be evaluated for importance based on the model AIC. Denominator degrees of freedom will be calculated using the Kenward-Roger small sample correction. The effects of site, therapist and their interaction with treatment will be included and tested. However, we do not anticipate any significant interactions or main effects of these factors given our balanced study design (equal numbers at each site in each group), our standard training and operating procedures at both sites and with all therapists, and our previous analyses from our similarly-designed study (our CCT for TBI study). In any case, the analysis procedures will include these factors and their interaction effects to avoid allowing site or therapist effects to bias treatment comparisons. If we detect any imbalances between the treatment groups, we will follow the primary analyses above with subsequent analyses considering the imbalances to verify that the conclusions are not affected by the imbalances. Analyses will be conducted within and across nested levels of the study design; this will involve within-subject analyses (comparison of occasions of measurement nested within an individual), as well as between-subject analyses. In addition, any treatment group comparison will be adjusted for subject-specific characteristics, and adjustments for changes in these characteristics over the course of the study can be incorporated into the single-subject analyses. **Power Analysis:** In addition to the procedures described by Hedeker and colleagues [94] for Random Regression Models (the RMASS program provided by Hedeker), we used several standard other methods for power calculation and estimation of needed sample size. We selected the sample size that would provide us with a minimum of 80% power across all hypotheses and their expected effect sizes. We used this method with the following assumptions to estimate required sample size: the mixed design of two groups (ME-CCT and SC) and time (4 levels, weeks 0, 4, 8, 21) where the slope is the dependent measure; alpha-level of .02, nature of the hypothesis (two-sided), dropout rate (up to 20%), autoregressive covariance structure (with correlation between sequential assessments set at .45) of the longitudinal data, medium effect size as a between-group difference increasing linearly from 0 at baseline to .5 SD units at the last time point, various correlations (.2, .5, and .8) between the repeated measures, and various effect sizes from medium to large. We estimated that with a final sample size of 180 participants (216, with a drop-out rate of 20%), the study will have

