
minimum 85% power to yield a statistically significant result for a medium effect size. As is noted in the previous sections, we have found medium to large post-treatment effect sizes for several outcome measures in our previous studies.

H2: Compared to those in SC, participants in ME-CCT will show significant improvements on measures of subjective cognitive complaints, subjective functioning, and collateral measures of everyday functioning.

Dependent variables: Subjective Everyday Functioning Composite Score (average total score across the two Neuro-QOL scales, namely the Applied Cognition Executive Function Scale, and the Applied Cognition General Concern Scale); ECog.

Independent variables: Treatment group (2 levels, ME-CCT and SC), and Time (4 levels, Weeks 0, 4, 8, 21). Statistical Analyses: Data will be analyzed similar to the method described for H1. Power Analyses: Power analyses were conducted similarly to H1, and the study will have 87% power to yield a statistically significant result for a medium effect size for H2. We have found large effects on subjective cognitive/functional complaints in previous studies.

H3: Compared to those in SC, participants in ME-CCT will show increased participation in protective activities, as measured by physical and cognitive activity inventories.

Dependent variables: Cognitive Activity Inventory, CHAMPS Physical Activity Inventory for Older Adults. Independent variables: Treatment group (2 levels, ME-CCT and SC), and Time (4 levels, Weeks 0, 4, 8, 21). Statistical Analyses: Data

will be analyzed similar to the method described for H1. Power Analyses: Power analyses were conducted similarly to H1, except the alpha level was set at .01; the study will have 80% power to yield a statistically significant result for a medium effect size for each dependent measure evaluated through H3.

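### Therapy groups of about six are randomised, but the power calculation has no group-level correlation, so the design does not deliver the stated 85%, 87% and 80% power

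*Combined protocol and SAP*

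**What the plan says.** **Randomisation (Section 9, Procedures).** New participants join a group that is waiting to be allocated. "Once group membership reaches the minimum of 6, the group will be randomized". The allocation list is also for groups: "For each site, groups will be randomly assigned to ME-CCT or SC based on the site's randomization table". Six is a minimum; no mean or maximum size is given. Both arms then receive eight weekly two-hour sessions in their group.

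**Numbers (Section 9, Recruitment and feasibility).** Enrolment is planned "for a total of 216 participants (108 ME-CCT and 108 SC").

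**Analysis (Hypothesis-specific data analysis plan, stage 3).** Mixed models are proposed to "account for clustering structure of the data (i.e., repeated assessments within an individual, groups, therapists and sites"). Under H1, random group-level effects are assessed by AIC, and degrees of freedom follow Kenward-Roger.

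**Power (H1, H2 and H3 paragraphs).** The target is a floor: "We selected the sample size that would provide us with a minimum of 80% power across all hypotheses and their expected effect sizes". The H1 inputs are two arms, four time points with slope as the outcome, two-sided alpha 0.02, dropout up to 20%, a 0.5 SD difference at the last time point, repeated-measures correlations of 0.2, 0.5 and 0.8, and an "autoregressive covariance structure (with correlation between sequential assessments set at .45) of the longitudinal data". For H1, with 180 people analysed, the plan concludes that it has "minimum 85% power to yield a statistically significant result for a medium effect size". H2 is stated at 87%, and H3 at 80% with alpha 0.01, both computed in the same way as H1.

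**The concern.** When whole groups are allocated, people in the same group share the assignment, and afterwards they share the therapist, the peers and the sessions. If their outcomes are positively correlated, the variance of the treatment contrast exceeds what 180 independent people would give. The test also rests on the number of groups rather than the number of people.

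The plan accepts this for the analysis but not for the power. All its listed correlations are within person. The plan mentions other standard power methods, but gives no group-level input for them. H2 and H3 inherit the gap because they follow the H1 method.

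The stated power is the plan's justification for its sample size. If it is too high, a null result on the co-primary outcomes would be read against an 85% claim that the design does not support.

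**Working it through.** **1. Reproduce the stated figure.** Take 90 per arm (180/2), a 0.5 SD difference and independent individuals.

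- Noncentrality = 0.5 × √(90/2) = 3.354.
- Alpha 0.02 (critical value 2.326): power = Φ(3.354 − 2.326) = 84.8%. The stated H1 figure is 85%.
- Alpha 0.01 (critical value 2.576): power = Φ(3.354 − 2.576) = 78.2%. The stated H3 figure is 80%.
- H2 at alpha 0.02 also gives 84.8%, so its stated 87% does not follow from these inputs.

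The H1 figure is therefore what an individually randomised comparison would give.

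**2. Count the randomised units.** 216/6 = 36 groups, 18 per arm. This is the most favourable count, because six is the minimum; groups of eight would give 27. With 180 analysed in 36 groups, m = 180/36 = 5 per group.

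**3. Back out the noncentrality from the stated powers.** This accepts the plan's own figures as correct at zero ICC.

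- H1: 2.326 + 1.036 = 3.363
- H2: 2.326 + 1.126 = 3.453
- H3: 2.576 + 0.842 = 3.417

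**4. Apply the design effect.** DE = 1 + (m − 1) × ICC. The noncentrality is divided by √DE. The ICC values are assumed, since the documents give none. Example for H1 with m = 5 and ICC 0.05: DE = 1 + 4 × 0.05 = 1.20; 3.363/√1.20 = 3.070; Φ(3.070 − 2.326) = 77.1%.

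| ICC (assumed), m = 5 | DE | Effective N (180/DE) | H1 | H2 | H3 |
|---|---|---|---|---|---|
| 0 (as stated) | 1.00 | 180 | 85.0% | 87.0% | 80.0% |
| 0.01 | 1.04 | 173 | 83.4% | 85.5% | 78.1% |
| 0.02 | 1.08 | 167 | 81.8% | 84.0% | 76.2% |
| 0.05 | 1.20 | 150 | 77.1% | 79.5% | 70.7% |
| 0.10 | 1.40 | 129 | 69.7% | 72.3% | 62.3% |

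With m = 6, ICC 0.05 gives DE 1.25 and 75.2%, 77.7% and 68.5%.

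**5. Use group-level degrees of freedom.** With 36 − 2 = 34 df and a noncentral t, the change of reference distribution alone gives 81.6%, 83.8% and 75.0% at zero ICC. At ICC 0.05 (m = 5) the figures are 73.3%, 75.8% and 65.2%.

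**6. Find where the 80% floor is crossed (normal approximation).** H1 needs DE = (3.363/(2.326 + 0.842))² = 1.127. That is an ICC of 0.127/4 = 0.032 for m = 5, or 0.127/5 = 0.025 for m = 6. H3 has no margin, so any positive ICC takes it below 80%.

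**7. Start from the plan's inputs instead of its stated powers.** With 90 per arm, 0.5 SD and m = 5, H1 and H2 are 81.6%, 76.9% and 69.4% at ICC 0.02, 0.05 and 0.10. H3 is 74.3%, 68.7% and 60.2%. The conclusion is unchanged and the figures are slightly lower.

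**The case against.** The strongest reply is that the analysis already handles clustering: group is a named level, random group effects are considered and Kenward-Roger is used, so what remains is an optimistic planning statement. This is partly right, since the fix changes no participant number or procedure. But it confirms that power was computed for a different model from the one planned. Dropping the group effect on AIC would not make members of a randomised group independent.

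Other points stand as limits on the size, not on the claim:

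- H1 is stated as at least 85%. If its true no-clustering power were 89%, H1 would reach 80% only at an ICC of about 0.064 (m = 5). The stated minimum is still breached in its worst scenario.
- The ICC is unknown. At 0.01 the loss is about two points. The design effect used is for a mean at one time; power was set for a slope, and the ICC of change could be smaller or larger.
- 34 df is the simple group-level count. Kenward-Roger df will depend on the fitted model, and part of the drop to 73% comes from the df, as step 5 separates.
- Clustering is not the only weakness. H3 reaches only 78.2% from the plan's inputs at zero ICC. A slope test under the stated autoregressive correlation gives only 57–65% at alpha 0.02. And 216 less 20% is 172.8, not 180. These faults push the true power lower; none offsets the omission.

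**Conclusion.** The concern holds. Groups are randomised, and no group-level term enters the power for H1, H2 or H3. The direction of the error is certain for any positive ICC; its size is not, because it depends on an ICC that the documents do not give. Over an assumed 0.01 to 0.10, with five analysed per group and the stated powers taken as correct at zero ICC, power falls to 83–70% for H1, 85–72% for H2 and 78–62% for H3. Group-level degrees of freedom lower these further. The 80% floor across all hypotheses is lost for H3 at once and for H1 above an ICC of about 0.03. Groups larger than six would raise the design effect and leave fewer units.

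**What to change.** In the power paragraphs for H1, H2 and H3:

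- State that randomisation is by therapy group, and give the planned number of groups (at most about 36 at six per group) and the expected group size.
- State an assumed ICC range, such as 0.01 to 0.10, with its justification.
- Multiply the variance by 1 + (m − 1) × ICC, use group-level degrees of freedom, and restate the power for each hypothesis over that range.
- Amend the sentence that claims at least 80% power for all hypotheses to match the result.

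The cost is a recalculation and a few sentences. The sample size stays as it is and no more participants are needed. The price is that the stated power becomes less favourable.

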improvements in objective cognitive performance and functional capacity. The frequency with which participants use these strategies will be evaluated with the Portland Cognitive Strategies Scale (PCSS) [69]. Our pilot data demonstrate significant increases in cognitive strategy use on the PCSS in Veterans with MCI following ME-CCT (see **Pilot Study 1**). We also found significantly increased strategy use on the PCSS in combat Veterans following CCT for TBI (see **Pilot Study 2**). Using the CHAMPS Physical Activity Questionnaire, the Fitbit data, and the Cognitive Activity Inventory, we will also evaluate whether increases in physical activity and mental activity mediate improvements in objective cognitive performance and functional capacity.

Baseline Characterization and Moderators (Exploratory Analyses). Baseline measures were selected to ensure that baseline rates of demographics, medical conditions, BMI, medication and substance use, psychiatric disorders, premorbid IQ, and significant other involvement are equivalent across groups. If between group analyses reveal any differences across groups in terms of these factors, they will be controlled for in subsequent analyses. In order to preliminarily explore for whom this intervention is most effective, we will evaluate whether these baseline variables (see **Table 5**) or baseline performance on primary and secondary endpoint measures moderate ME-CCT associated improvements in objective cognitive performance and functional capacity.

HYPOTHESIS-SPECIFIC DATA ANALYSIS PLAN AND POWER ANALYSES

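### The H1 analysis set drops randomised participants with no post-baseline evaluation; the model does not need this, and no all-randomised analysis is stated

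*Combined protocol and SAP*

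**What the plan says.** Section 9, H1 Statistical Analysis, defines the set: "We will analyze data on all randomized subjects for whom we have a baseline assessment and at least one post-baseline evaluation". The H2 and H3 paragraphs refer back to the H1 method and give no population of their own. Time has four levels, including Week 0, and "A fully saturated treatment X time model will be utilized for inference".

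Under Procedures, the baseline visit comes first, and a group is randomised once it reaches at least six members. Table 5 lists both co-primary composites at weeks 0, 8 and 21 only. Assessment Methodology confirms that performance tests are not given at week 4.

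Several parts of the plan bear on missing data or imbalance:

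- Stage 3 of the data analysis plan favours mixed models partly because the approach "allows the inclusion of subjects with missing data or those who were terminated early in the study".
- Stage 4 adds pattern-mixture models "to assess if there is bias due to drop out or missing data".
- Stage 2 says: "Any statistically and clinically significant differences will be controlled for in subsequent analyses by adding the target variables as covariates to the model".
- Baseline Characterization and Moderators says: "If between group analyses reveal any differences across groups in terms of these factors, they will be controlled for in subsequent analyses". Its list of factors does not include the baseline composite.
- H1 says "any treatment group comparison will be adjusted for subject-specific characteristics" and, if imbalances are found, promises "subsequent analyses considering the imbalances to verify that the conclusions are not affected by the imbalances".
- Section 9.9 allows session attendance as a covariate in unspecified final analyses, where suitable.

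**The concern.** Whether someone returns for an evaluation is decided after randomisation and may depend on the arm. A set defined that way no longer has the balance that randomisation gives. The plan states no all-randomised analysis to set beside it.

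The rule also works against the plan's own reason for using a mixed model. With Week 0 as a response, a participant seen only at baseline supplies a usable value. The filter removes the earliest leavers, whom the model was chosen to keep.

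For the co-primaries the rule can be read two ways. Take two participants who each have only a baseline composite, one of whom also completed a week-4 questionnaire. Their H1 data are identical, yet one may be in and the other out. COVID Procedures adds a further case: some follow-up may be collected remotely, without saying whether the co-primary tests are included. Two analysts could build different H1 sets.

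Attendance is a secondary point. It is measured after randomisation, and nothing keeps it out of the ME-CCT versus SC comparison. No size is claimed for this.

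**Working it through.** **How many could be excluded.** The plan gives 216 recruited, 20% drop-out and a final 180. These do not agree: 216 × .80 = 172.8, while 216 − 180 = 36 (16.7%). They bound the number at 36 to 43 (216 × .20 = 43.2). It is lower if people leave before their group is randomised, have a later composite, or count through a week-4 visit.

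**Bias from dropping baseline-only participants.** Assumptions: no true effect; scores y0 (baseline) and y8 (week 8) with unit variance and correlation ρ; log-odds of loss rising by .5, 1 or 1.5 per SD lower baseline (odds ratios 1.65, 2.72, 4.48). The ρ values (.2, .45, .5, .8) are those in the H1 power paragraph. Loss rates by arm are assumed.

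Among those followed, an arm's expected change from week 0 to week 8 is −(1 − ρ) × its mean y0. So the size of the bias is (1 − ρ) × D, where D is the arm difference in mean y0 among those followed. It goes against the arm with the heavier baseline-dependent loss.

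For 20% v 10% loss at slope 1.5, the followed means are .227 and .122, so D = .105. At ρ = .45 the bias is .55 × .105 = .058.

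| Slope | D, 20% v 10% | ρ=.2 | ρ=.45 | ρ=.5 | ρ=.8 |
|---|---|---|---|---|---|
| 0.5 | .047 | .038 | .026 | .024 | .009 |
| 1.0 | .082 | .066 | .045 | .041 | .016 |
| 1.5 | .105 | .084 | .058 | .052 | .021 |

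- *Extreme case:* 20% loss in each arm, baseline-dependent in one and random in the other. D is .096, .173 and .227. The bias is .019 to .125 for ρ of .45 to .8, and .077 to .181 at ρ = .2.
- *Same rate and same dependence in both arms, or completely random loss:* zero.
- *Week 21, for someone never followed:* the same formula with the baseline to week-21 correlation. Under the autoregressive .45 assumption with three composite occasions, .45² = .20, so the ρ = .2 column applies.

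**Keeping baseline-only participants.** Under baseline-dependent loss the expected bias is zero. In simulation (108 per arm, 8,000 trials per setting) the kept set was within .004 SD of zero. So was a model of post-baseline scores adjusted for baseline.

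**When keeping them does not help.** If 20% loss in one arm depends on the unseen week-8 score and loss in the other is random, the bias for ρ of .45 to .8 is .019 to .125 with these participants dropped and .035 to .188 with them kept.

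**Do the planned adjustments repair it?** A baseline covariate entered as a main effect, with Week 0 also a response, shifts all of a person's values equally. The within-person change does not move. In two simulated data sets (4,000 per arm, slope 1.5, 20% v 10%) the treatment × time estimate was −.02845 (ρ = .45) and −.01793 (ρ = .8), both with and without the covariate. As a baseline × time term it gave .006 and .004.

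The significance trigger would rarely fire. The assumed test is two-sided at .05 on the baseline score, with 108 × .8 ≈ 86 and 108 × .9 ≈ 97 followed. The standard error is √(1/86 + 1/97) = .148. For D = .047, .082 and .105, detection is 6%, 9% and 11%. In the extreme case (86 v 86) it is 10%, 21% and 32%.

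**The case against.** The best case against is about weight.

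- **Size.** At 20% v 10% loss and no clustering, the standard error of the week-8 contrast is √(2(1 − ρ)(1/86.4 + 1/97.2)), which is .155 at ρ = .45 and .094 at ρ = .8. The bias is then about 0.1 to 0.4 standard errors. Two-sided type I error moves from .020 to .021–.029, or up to .033 at ρ = .2. Clustering by group would dilute this further.
- **Loss rates.** The team's earlier experience was 10 to 11%. At 10% v 5% the same formula gives .005 to .031 SD. All earlier non-completers in the mild TBI trial left before the group began, so some comparable leavers here may never be randomised.
- **Design.** Equal contact in the control arm, make-up sessions and reminder calls all work against unequal loss.
- **Convention.** Requiring one post-baseline value is a common modified intention-to-treat rule. The wider set is worse if loss depends on the unseen score.
- **Reach.** H2 and H3 outcomes are measured at week 4, so fewer participants would be excluded there. The reference to H1 does not expressly carry over the population.

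The points on size and loss rates stand and keep this from being a serious defect. The point about the unseen score also stands, and is why the wider set needs a sensitivity analysis. The rest does not remove the concern. Retention measures lower the count but restore nobody. The pattern-mixture text names neither its population nor a no-follow-up pattern. An outcome-specific reading of the rule is plausible, but it is not written.

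**Conclusion.** The concern holds. H1 is conditioned on a post-randomisation event, the condition is unclear for the co-primaries, and no all-randomised analysis is stated. H2 and H3 appear to inherit the rule.

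The likely size is modest: .01 to .06 SD at week 8 for 20% v 10% baseline-dependent loss and correlations of .45 to .8 (.04 to .08 at .2). The constructed extreme gives .02 to .12 SD (.08 to .18 at .2). All of this is small beside the planned .5 SD. The figures rest on assumed loss rates and dependence, unit variances, no true effect, and every lost participant having no follow-up composite. The true number affected is unknown.

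The wider set is better under baseline-dependent unequal loss, neutral when loss is random or alike in both arms, and worse when loss depends on the unseen outcome. The change is worth making because it is cheap and fixes the analysis set in advance. The trial is not unsound without it.

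**What to change.** 1. In H1, remove the requirement for a post-baseline evaluation. The primary set becomes all randomised participants with a baseline assessment, analysed in the arm allocated, with Week 0 kept as a response. State that H2 and H3 use the same set.
2. Run the planned pattern-mixture analysis on that set. Define a pattern for participants with no follow-up composite (none at week 8 or week 21), and state the assumption made about their missing scores.
3. Report by arm how many randomised participants have no post-baseline composite.
4. In Section 9.9, add that attendance will not be a covariate in the ME-CCT versus SC efficacy comparisons and will be used only descriptively or in labelled exploratory analyses.

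The cost is a few sentences and a little more analysis. No new data are needed, because baseline is collected before the group is randomised. The downside is that the primary analysis then relies on missing at random for people never seen again, which step 2 is there to test.
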